#### 15.3.6.3. Clinical Laboratory Assessments

Clinical laboratory parameters will be summarized by presenting shift tables and through by visit summaries of the observed values including the Week 24 LOCF endpoint along with change from Baseline values. Both the PS Baseline and the OLE Baseline will be used in the calculation of change values. For parameters with categorical outcomes, the number and percentage of subjects with each outcome will be summarized by visit. The number and percentage of subjects

with at least one potentially clinically significant (PCS) value post-OLE Baseline for selected parameters will also be presented. PCS criteria for clinical laboratory parameters will be provided in the statistical analysis plan (SAP).

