The current standard of care for the treatment of schizophrenia is the use of second generation antipsychotics or "atypical antipsychotics" (Lehman-2004; Kreyenbuhl-2009; Meltzer-2011; Nakamura-2009). These "atypicals" are thought to have fewer extrapyramidal side effects compared to first generation antipsychotics or "typical antipsychotics" (eg, haloperidol) (Leucht-2009; Naber-2009). However, some patients respond poorly to both atypical and typical antipsychotics, and some continue to have symptoms and substantial functional/cognitive impairment (Keefe-2006; Webber-2008). Very few patients return to baseline (pre-psychosis) function (Schultz-1999; Pearlson-2000; Kapur-2001). In addition, some atypical agents are associated with a variety of other side effects, including weight gain, metabolic syndrome, sedation, QTc prolongation, extrapyramidal symptoms and tardive dyskinesia (Davis-2004; Lieberman-2005; Newcomer-2007; Leucht-2009), which may lead to significant comorbid medical problems as well as contribute to poor compliance and treatment discontinuation.

The large-scale NIMH-CATIE schizophrenia study found that 70% to 80% of outpatients discontinue medications before 18 months because of lack of efficacy or occurrence of side effects (Lieberman-2005). Noncompliance often leads to relapse of symptoms and the need for rehospitalization (Ascher-Svanum-2010; Munro-2011; Morken-2008). Clearly, an unmet need exists for new, effective, and well-tolerated treatments for schizophrenia.

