#### **15.3.6.5.** Vital Signs

Vital sign parameters will be summarized by presenting by visit and Week 24 LOCF endpoint summaries of the observed values and the change from Baseline values. Both the PS Baseline and the OLE Baseline will be used in the calculation of change values. For adolescent subjects, height will also be summarized. In addition, the number and percentage of subjects with at least one PCS value post-OLE Baseline for selected parameters will be presented. PCS criteria for the vital sign parameters will be provided in the SAP.

Orthostatic hypotension is defined as a decrease of  $\geq 20$  mmHg in systolic blood pressure or  $\geq 10$  mmHg in diastolic blood pressure after a subject has been standing for at least 2 to 4 minutes, compared to the systolic blood pressure and diastolic pressure measured in the supine position, respectively. Orthostatic tachycardia is defined as a pulse rate increase of  $\geq 20$  bpm and a pulse rate of > 100 bpm after a subject has been standing for at least 2 to 4 minutes, compared to the pulse rate measured in the supine position.

The number and percentage of subjects with orthostatic hypotension and orthostatic tachycardia will be summarized for Baseline and the overall post-OLE Baseline period, as well as by visit.

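### The PCS laboratory and vital-sign counts do not separate new abnormalities from those already present at PS or OLE Baseline

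*Protocol*

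**What the plan says.** For laboratory data, Section 15.3.6.3 plans a tabulation of subjects "with at least one potentially clinically significant (PCS) value post-OLE Baseline for selected parameters". For vital signs, Section 15.3.6.5 plans the same: "the number and percentage of subjects with at least one PCS value post-OLE Baseline for selected parameters will be presented". Neither section refers to the subject's PCS status at either baseline.

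The thresholds are deferred. For vital signs the protocol states that "PCS criteria for the vital sign parameters will be provided in the SAP", and Section 15.3.6.3 does the same for laboratory parameters.

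Other displays do use baseline. For laboratory data, "Clinical laboratory parameters will be summarized by presenting shift tables" is planned alongside by-visit summaries. In both sections changes are taken from two reference points: "Both the PS Baseline and the OLE Baseline will be used in the calculation of change values". Section 15.3.6.5 also tabulates orthostatic hypotension and orthostatic tachycardia at Baseline as well as afterwards. It plans no shift table for vital signs.

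**The concern.** Subjects enter after an 8-week parent study in which they were switched from another antipsychotic (Sections 4.2 and 7.1). The protocol notes that "some atypical agents are associated with a variety of other side effects, including weight gain, metabolic syndrome" and further effects. Appendix II includes glucose, HbA1c, lipids and prolactin, so some subjects may plausibly arrive with values that have been abnormal for some time. Exclusion criterion 2 in Section 8.2 names physical examination, vital-sign and ECG findings, as judged by the investigator. It does not name laboratory values.

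A PCS percentage that combines persisting and new abnormality is hard to interpret in a single-arm study whose purpose is long-term safety. The reader cannot tell whether 10 subjects with a PCS value means 10 new findings or 3. Elsewhere the protocol makes the distinction. Section 15.3.6.2 restricts AE summaries to new events and sends carried-over AEs to listings. Section 15.3.6.4 pairs absolute QTc limits with categories of change from both baselines. The PCS counts have neither a baseline condition nor a stated baseline counterpart.

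**Working it through.** **1. Who is counted.** The possible patterns of PCS status for one parameter are set out below, with the planned count and two baseline-conditioned counts.

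| PCS at PS Baseline | PCS at OLE Baseline | PCS after OLE Baseline | Planned count | Count among not PCS at PS | Count among not PCS at OLE |
|---|---|---|---|---|---|
| No | No | Yes | Yes | Yes | Yes |
| No | Yes | Yes | Yes | Yes | No |
| Yes | No | Yes | Yes | No | Yes |
| Yes | Yes | Yes | Yes | No | No |
| Either | Either | No | No | No | No |

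The planned count merges the first four rows. The second row is an abnormality that arose during the parent study and persisted. A count conditioned on OLE Baseline alone would omit it.

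**2. The planning figure.** The only number the protocol supplies is the expected enrolment: 120 × 0.75 × 0.75 = 67.5, stated as approximately 67 (synopsis and Section 15.1). It reproduces.

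**3. Illustration of size.** The protocol gives no PCS thresholds, baseline prevalence or persistence, so the inputs below are assumptions:

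- b = share PCS at OLE Baseline: 0% to 20%
- s = share of those who are PCS again afterwards: 50% to 100%
- r = share of the remaining subjects who become PCS: 5%
- all 67 subjects have a post-OLE Baseline value

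Planned proportion = b·s + (1 − b)·r. New cases = 67·(1 − b)·r, out of 67·(1 − b) subjects not PCS at OLE Baseline. The carried-over share of the count is b·s divided by the planned proportion.

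For b = 10%:

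- s = 50%: 0.05 + 0.045 = 0.095, and 67 × 0.095 = 6.4 subjects.
- s = 100%: 0.10 + 0.045 = 0.145, and 67 × 0.145 = 9.7 subjects.
- New cases in either case: 67 × 0.045 = 3.0, out of 60.3.

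| b | Planned count, s = 50% | Planned count, s = 100% | New cases | Carried-over share of the count |
|---|---|---|---|---|
| 0% | 3.4 (5.0%) | 3.4 (5.0%) | 3.4 of 67 | 0% |
| 5% | 4.9 (7.3%) | 6.5 (9.8%) | 3.2 of 63.6 | 34% to 51% |
| 10% | 6.4 (9.5%) | 9.7 (14.5%) | 3.0 of 60.3 | 53% to 69% |
| 20% | 9.4 (14.0%) | 16.1 (24.0%) | 2.7 of 53.6 | 71% to 83% |

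The same formula applies to PS Baseline if b is read as the share PCS at that visit.

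**The case against.** The strongest reply is that this belongs to the SAP. The protocol defers PCS criteria, not merely numerical limits, and the SAP could add a change-from-baseline component or a baseline restriction. That possibility stands, and nothing in the two sections prevents a display by baseline status. But the rule for whom to count is already written in the protocol, and a SAP that followed it literally would merge persisting and new cases.

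A second reply is that baseline status is visible elsewhere. The laboratory shift tables and the changes from both baselines do help. Clinically significant changes since consent are also recorded as AEs (Sections 11.3.2, 11.3.3 and 12.2), and AE summaries cover only new events. These mitigate the problem but do not remove it. The shift tables are not stated to use PCS categories, vital signs have none, mean changes do not identify individual subjects, and AE recording depends on investigator judgement rather than PCS criteria.

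A reader might infer three stronger points, which the documents do not support:

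- That every subject abnormal before the first OLE dose is counted. A PCS value after OLE Baseline is required, so a subject who normalizes and stays normal is not counted.
- That the protocol misreports the rate caused by the extension. It never calls this count new, emergent or attributable.
- That only abnormality new since OLE Baseline matters. Subjects are already taking SEP-363856 at OLE Baseline and continue at the same dose (Section 10.1.1), so a value abnormal at that visit may itself have arisen on the drug.

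**Conclusion.** The point holds as a minor improvement. As worded, the PCS counts combine carried-over and new abnormality, and the planned displays do not fully separate them, least of all for vital signs. No figure in the protocol is wrong, and the primary endpoint, AE incidence, is unaffected.

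The size cannot be computed from the document. The effect is zero when nobody is PCS at baseline. With 67 subjects, 5% new PCS, 10% baseline PCS and 50% to 100% persistence, about 6 to 10 subjects are counted against about 3 new, a ratio of roughly 2.1 to 3.2 (0.095/0.045 and 0.145/0.045). A ratio near 6 arises only at 20% baseline prevalence with full persistence (0.24/0.04). A reader should not take that extreme as an estimate, because both inputs are assumed.

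**What to change.** In Sections 15.3.6.3 and 15.3.6.5, keep the planned any-value count and add two rows for each selected laboratory and vital-sign parameter:

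1. subjects with a post-OLE Baseline PCS value among those not PCS at PS Baseline;
2. the same among those not PCS at OLE Baseline.

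Each denominator should be the subjects with a non-PCS value at that baseline and at least one later value. Report both rows. The OLE Baseline row should not stand alone as the main result, because that visit is already on study drug and the row would omit abnormalities that began in the parent study and persisted.

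Values at both baselines are already used for change scores, so no new data are needed. The cost is extra table rows and slightly smaller denominators, for example about 60 rather than 67 if 10% are PCS at the reference visit.

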#### 15.3.6.4. ECGs

ECG analysis will be based on the centrally read data. Observed values and changes from Baseline in ECG parameters will be summarized. In addition, the number and percentage of subjects with prolonged QTc intervals (> 450 msec, > 480 msec, and > 500 msec) and changes in QTc intervals  $\geq$  30 but < 60 msec and  $\geq$  60 msec will be summarized. Fridericia's correction (QTcF) and Bazett's correction (QTcB) will be used for QT interval correction. Both the PS Baseline and the OLE Baseline will be used in the calculation of change values.

#### **15.3.6.5.** Vital Signs

Vital sign parameters will be summarized by presenting by visit and Week 24 LOCF endpoint summaries of the observed values and the change from Baseline values. Both the PS Baseline and the OLE Baseline will be used in the calculation of change values. For adolescent subjects, height will also be summarized. In addition, the number and percentage of subjects with at least one PCS value post-OLE Baseline for selected parameters will be presented. PCS criteria for the vital sign parameters will be provided in the SAP.

Orthostatic hypotension is defined as a decrease of  $\geq 20$  mmHg in systolic blood pressure or  $\geq 10$  mmHg in diastolic blood pressure after a subject has been standing for at least 2 to 4 minutes, compared to the systolic blood pressure and diastolic pressure measured in the supine position, respectively. Orthostatic tachycardia is defined as a pulse rate increase of  $\geq 20$  bpm and a pulse rate of > 100 bpm after a subject has been standing for at least 2 to 4 minutes, compared to the pulse rate measured in the supine position.

The number and percentage of subjects with orthostatic hypotension and orthostatic tachycardia will be summarized for Baseline and the overall post-OLE Baseline period, as well as by visit.

#### 15.3.6.6. Physical and Neurological Examination

Clinically significant findings from the physical and neurological examination at the extension visits will be captured as AEs as appropriate and summarized together with the other AEs.

#### 15.3.6.7. Concomitant Medications

All medications will be coded to indication-specific ATC (Anatomical Therapeutic Chemical) classification (ie, ATC level 3) and preferred name using the World Health Organization Drug Dictionary (WHO-DD).

Any medications taken during the course of the open-label extension study, with a start date/time on or after the first dose of the open-label extension study drug and on or before the last dose of the open-label extension study drug; or with a start date/time prior to, and an end date/time on or after, the first dose of the open-label extension study drug, or marked as ongoing, will be considered concomitant medications. Medications that ended prior to the first dose of the open-label extension study drug will be considered prior medications. Medications that started after the last dose of the open-label extension study drug will not be considered concomitant but

will be considered post-treatment. Prior and Concomitant medications will be summarized for the number and percentage of subjects using each medication and by the drug class and preferred name for the safety population.

## 15.3.6.8. Suicidality Measure

Frequency and severity of suicidal ideation and suicidal behavior as measured by the C-SSRS scale will be summarized for the overall post-OLE Baseline period, by visit, and by telephone contact week.

#### 15.3.6.9. Measures of Motor Function

Measures of motor function include SAS, BARS and AIMS. The observed values of SAS mean score, BARS total score and AIMS total score at the PS Baseline, OLE Baseline, and each scheduled post-OLE Baseline extension visit that it is scheduled for collection, including the Week 24 LOCF endpoint, will be summarized. Changes from Baseline in these measures will also be summarized for each scheduled post-OLE Baseline extension visit, using both the PS Baseline and the OLE Baseline.

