**Table 2: Schedule of Assessments** 

Procedures			Tre	atment Per	iod			Follow-up Period
	V1E	V2E	V3E	V4E	V5E	V6E	V7E	V8E
	OLE Baseline a	Week 4	Week 8	Week 12	Week 16	Week 20	Week 24 EOT/ ET b	Follow-up EOS c
Study Day	Day 1	Day 29 ±3 days	Day 57 ±3 days	Day 85 ±3 days	Day 113 ±3 days	Day 141 ±3 days	Day 169 ±3 days	7±2 days after last dose
Informed consent	X							
Inclusion/exclusion criteria	X							
Concomitant medication review d	X	X	X	X	X	X	X	X
Dispense study drug e	X	X	X	X	X	X		
Study drug accountability		X	X	X	X	X	X	
Telephone contacts f			duled visits					
Physical/neurological examination	Core	X		X			X	X
Nicotine use information	Core			X			X	
Vital signs g	Core	X	X	X	X	X	X	X
Weight (including BMI h)	Core	X	X	X	X	X	X	
Height i	Core Pre- switch screening							
Waist circumference	Core	X		X			X	
12-lead Electrocardiogram (ECG)	Core	X		X			X	
Hematology, chemistry, urinalysis j	Core	X		X			X	
Blood sample for PK k	Core	X		X			X	
Urine drug screen 		X		X			X	
Rapid urine drug screen 	Core							
Serum β-hCG, females only	Core							
Urine β-hCG, females only m		X	X	X	X	X	X	X
Rapid urine β-hCG, females only m	Core							
Positive and Negative Syndrome Scale (PANSS)	Core	X	X		X		X	
Clinical Global Impression – Severity (CGI-S)	Core	X	X		X		X	

**Table 2:** Schedule of Assessments (Continued)

Procedures			Tre	atment Peri	iod			Follow-up Period
	V1E	V2E	V3E	V4E	V5E	V6E	V7E	V8E
	OLE Baseline a	Week 4	Week 8	Week 12	Week 16	Week 20	Week 24 EOT/ ET b	Follow-up EOS c
Study Day	Day 1	Day 29 ±3 days	Day 57 ±3 days	Day 85 ±3 days	Day 113 ±3 days	Day 141 ±3 days	Day 169 ±3 days	7±2 days after last dose
Clinical Global Impression – Improvement (CGI-I)	Core	X	X		X		X	
Brief Negative Symptom Scale (BNSS)	Core	X	X		X		X	
Columbia Suicide Severity Rating Scale (C-SSRS)	Core	X	X	X	X	X	X	X
Simpson-Angus Scale (SAS) n	Core	X					X	
Barnes Akathisia Rating Scale (BARS) n	Core	X					X	
Abnormal Involuntary Movement Scale (AIMS) n	Core	X					X	
Pittsburgh Sleep Quality Index (PSQI)	Core			X			X	
Personal and Social Performance Scale (PSP)	Core			X			X	
Short Form Health Survey (SF-12)	Core						X	
Medication Satisfaction Questionnaire (MSQ)	Core						X	
Healthcare Resource Utilization (HCRU), since last assessment	Pre-switch Baseline visit of Core			X			X	

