- j Subjects must be fasted (no food or drink except water at least 8 hours prior to clinical laboratory tests). A list of clinical laboratory tests is provided in Section 21.
- k Blood samples for plasma concentrations of SEP-363856 will be collected on Day 29, Day 85 and Day 169/EOT/ET. The time and date of the previous dose of study drug prior to blood sampling and the time and date of blood sampling must be recorded. The remaining plasma samples, after PK measurement is completed, CCI
-  Urine drug screen may be ordered at other visits as deemed clinically appropriate. These results should be discussed with the Medical Monitor.
- m Any positive urine β-hCG test should be confirmed by a serum β-hCG test.
- n Unscheduled SAS, BARS and AIMS scales should be administered if a subject develops extrapyramidal symptoms requiring treatment.
- o Any new AEs occurring after signing the informed consent form for this study (SEP361-309) at V1E will be collected. Adverse events with onset during the Core study (SEP361-308) and ongoing at the start of the current study (SEP361-309) will be entered into the eCRF.

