### 10.3.3. Allowed Concomitant Psychotropic Medications

Subjects are permitted to remain on non-prohibited psychotropic medications that have been part of their ongoing treatment regimen prior to and during SEP361-308. Treatment with benztropine (benzotropine outside the US) up to 6 mg/day is permitted, as needed, for motor symptoms. In cases where benztropine is not available or a subject has had an inadequate response or intolerability to benztropine treatment, the following medications may be used to treat acute extrapyramidal symptoms (EPS): biperiden (up to 16 mg/day) or trihexyphenidyl (up to 15 mg/day) or diphenhydramine (up to 100 mg/day). Treatment with propranolol (up to 120 mg/day) is permitted as needed for akathisia. These allowed medications for the treatment of EPS and akathisia may be given in any formulation (oral, intramuscular [IM] or intravenous [IV]) as deemed appropriate by the investigator. Medications used to treat motor symptoms should not be given prophylactically.

Concomitant use of lorazepam, temazepam, eszopiclone, zaleplon, zolpidem and zolpidem controlled release (CR) is permitted at the discretion of the Investigator with the following restrictions:

- Oral lorazepam is permitted for clinically significant anxiety/agitation or as a sedative/hypnotic up to a maximum daily dose of 6 mg/day. Intramuscular (IM) lorazepam is permitted up to 4 mg/day for acute anxiety/agitation, as clinically indicated. Lorazepam should be used sparingly, when clinically required, per investigator judgment.
- Temazepam (≤ 30 mg/day), eszopiclone (≤ 3 mg/day), zopiclone (≤ 7.5 mg/day), zaleplon (≤ 20 mg/day), zolpidem (≤ 10 mg/day), and zolpidem CR (≤ 12.5 mg/day) may be administered at bedtime for insomnia, as needed.
- Diphenhydramine ≤ 100 mg/day and melatonin ≤ 10 mg/day may be administered at bedtime for insomnia, as needed. Over-the-counter melatonin may be used. Combination melatonin products are not allowed.
- Medications that are used for insomnia should be administered no more than once nightly and should not be used in combination.
- Medications used for the treatment of anxiety/agitation and insomnia (eg, lorazepam and zolpidem) should not be used in close temporal proximity (defined as administration within 2 hours of each other).

Similar drugs at equivalent dosages may be permitted after consultation with the Medical Monitor.

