# 15.3.10. Treatment of Missing Data

For scales with more than one item, such as PANSS, if any item score contributing to the total/subscale score is missing, the total/subscale score will be set to missing.

Missing data at Week 24 will be imputed using the LOCF approach. The LOCF endpoint is defined as the last non-missing value at a scheduled or unscheduled visit post-baseline during the treatment period excluding the Follow-up Visit.

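### Symptom-triggered SAS, BARS and AIMS ratings reach the motor summaries only when they are a subject's last treatment-period value, so the change-in-scale endpoint understates transient, treated motor worsening

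*Protocol*

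**What the plan says.** Protocol Table 2 schedules the three movement scales after OLE Baseline at Week 4 (Day 29) and at Week 24/EOT/ET (Day 169), and at no visit between. The visit lists in sections 11.6.2 to 11.6.7 agree. Footnote n of the table adds: "Unscheduled SAS, BARS and AIMS scales should be administered if a subject develops extrapyramidal symptoms requiring treatment".

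A subject with such symptoms may stay in the study on treatment. Section 10.3.3 says: "Treatment with benztropine (benzotropine outside the US) up to 6 mg/day is permitted, as needed, for motor symptoms". It also lists alternatives to benztropine, and propranolol for akathisia.

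Section 15.3.6.9 fixes the summaries. Observed SAS mean, BARS total and AIMS total are taken at the two baselines and "each scheduled post-OLE Baseline extension visit that it is scheduled for collection, including the Week 24 LOCF endpoint, will be summarized". For change, it says: "Changes from Baseline in these measures will also be summarized for each scheduled post-OLE Baseline extension visit, using both the PS Baseline and the OLE" (so both baselines serve as reference).

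Section 15.3.10 says "Missing data at Week 24 will be imputed using the LOCF approach" and defines the LOCF endpoint as the "last non-missing value at a scheduled or unscheduled visit post-baseline during the treatment period excluding the Follow-up Visit".

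Change in the three scales from both baselines is a named safety endpoint (section 6.2), and the scales are listed among the objectives (section 5.2).

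**The concern.** Data collection and analysis do not fit together here. Footnote n asks for all three scales at the moment a motor problem is bad enough to treat. Those are the ratings most likely to show a motor effect, and they are the only SAS, BARS and AIMS scores that can fall between Week 4 and Week 24/ET. Yet section 15.3.6.9 has no summary to which an unscheduled rating contributes in its own right.

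At stake is how the motor endpoint reads. A subject who is unremarkable at Week 4, worsens in Week 10, is treated and improves by Week 24 contributes two unremarkable scores. The high score has been collected but is not summarised. The study is single-arm and descriptive, so a reader has no comparator against which to notice that the by-visit figures leave out treated episodes.

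**Working it through.** **1. The plan's own figure.** Sections 8.1 and 15 are not needed for this; the synopsis gives 120 subjects in the core study, 75% completing and 75% of completers enrolling. 120 × 0.75 × 0.75 = 67.5, against about 67 stated. It serves below only as a denominator.

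**2. The gap between scheduled motor ratings** (Table 2).
- Nominal: 169 − 29 = 140 days, or 140 / 7 = 20 weeks.
- Treatment period: 24 × 7 = 168 days, so 140 / 168 = 83%.
- With ±3-day windows: shortest (169 − 3) − (29 + 3) = 134 days; longest (169 + 3) − (29 − 3) = 146 days.

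**3. Where an unscheduled rating can go under sections 15.3.6.9 and 15.3.10.**
- *Subject completes and is rated at Week 24.* The Week 24 value is not missing and is also the last value. The unscheduled score is in no motor-scale summary.
- *Subject discontinues and has the ET visit.* Table 2 footnote b asks for all ET procedures within 48 hours of the last dose, and section 11.6.7 includes the three scales. The ET rating is later and replaces the unscheduled one. If the subject stops soon after the motor event, the ET score may itself show it.
- *Subject has no motor rating after the unscheduled one.* The unscheduled score is the last non-missing value and enters the Week 24 LOCF summary of observed values.

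The loss therefore falls mainly on subjects who are treated, stay on and are rated again. Their later score may be made on EPS medication.

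One detail is left open. In section 15.3.6.9 the sentence on observed values names the LOCF endpoint, while the sentence on change does not. The general rule in section 15.3.10 may cover change as well.

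**4. Comparison with the other safety summaries.**

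| Section | Any-time post-OLE Baseline summary planned? |
|---|---|
| 15.3.6.8 C-SSRS | Yes, overall period as well as by visit and call |
| 15.3.6.3 Laboratory | Yes, subjects with at least one potentially clinically significant (PCS) value |
| 15.3.6.5 Vital signs | Yes, subjects with at least one PCS value; orthostatic events over the overall period |
| 15.3.6.9 SAS, BARS, AIMS | No |

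**5. How many subjects, by assumption.** The documents give no rate of treated EPS, so both inputs are assumed: p, the share of 67 subjects with treated EPS and an unscheduled rating; and q, the share of those with no later Week 24/ET rating. Subjects in no motor-scale summary = 67 × p × (1 − q).

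| p | Subjects with treated EPS | Not summarised, q = 0 | Not summarised, q = 50% |
|---|---|---|---|
| 2% | 1.3 | 1.3 | 0.7 |
| 5% | 3.4 | 3.4 | 1.7 |
| 10% | 6.7 | 6.7 | 3.4 |

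The range is about 0.7 to 6.7 subjects. The effect on mean change cannot be computed, because the documents give no scale values.

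**The case against.** The strongest reply is that the trial does not lose the event. EPS that needs treatment and is reported as an adverse event counts in the primary endpoint (section 15.3.6.1) and is tabulated by class, term, severity, relationship and modal dose (15.3.6.2). The medicines used are tabulated too (15.3.6.7). A reader might infer that treated EPS vanishes from the safety results. The documents do not support that; only the scale scores are affected.

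A reader might also infer that unscheduled ratings are excluded altogether, or that motor function goes unobserved for 20 weeks. Neither holds. The LOCF definition expressly admits unscheduled values. Week 12 has a scheduled neurological examination covering motor system, coordination and gait (11.3.5, 11.6.4), and adverse events are collected at every visit and in the weekly calls (11.6.8).

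Two further points have weight. The SAP, which is not shown, could add a worst-value table, and section 15 leaves methodological detail to it. But section 15.3.6.9 states which time points are summarised and, unlike 15.3.5.2, 15.3.6.3 and 15.3.6.5, makes no deferral of its own to the SAP. This is a stated choice of time points, not an absent detail.

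Second, a maximum has its own bias. It is less favourable by construction, and only subjects with treated EPS receive extra ratings, so ascertainment is uneven and no comparator offsets it. That stands, and it is why the maximum should sit beside the by-visit tables and not replace them.

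**Conclusion.** The point holds in a limited form. Under the protocol as written, a symptom-triggered SAS, BARS or AIMS score followed by a Week 24 or ET rating enters no motor-scale summary, so the change-in-scale endpoint understates transient, treated motor worsening. The 140-day interval (83% of treatment) follows directly from the schedule. The number of subjects affected, about 0.7 to 6.7 of 67, rests wholly on assumed rates of 2% to 10% and an assumed 0% to 50% without a later rating.

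The conclusion also assumes that footnote n is followed and that no summary beyond those in section 15.3.6.9 is added elsewhere. It does not extend to the primary endpoint or to the adverse event and medication tables. This is a cheap improvement to a secondary safety summary, not a flaw that changes what the trial can conclude overall.

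**What to change.** In section 15.3.6.9, keep the by-visit and LOCF tables. Add, for SAS mean score, BARS total score and AIMS total score, the maximum post-OLE Baseline value over all scheduled and unscheduled treatment-period ratings, with its change from PS Baseline and from OLE Baseline.

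Label the table as a worst-value summary, and note that it is less favourable by construction and includes symptom-triggered ratings only for subjects with treated EPS. Do not add a count of subjects with any worsening unless a threshold is pre-specified; over an uneven number of ratings, such a count would pick up ordinary rating variation.

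The cost is one extra summary per scale from data already collected. No assessment, visit or clinical rule changes.
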